Demographic and clinical data were recorded. Dyspnea was assessed by the modified Medical Research Council (mMRC) dyspnea questionnaire (11) and quality of life by the COPD Assessment Test (CAT) questionnaire (12). Spirometry was performed according to American Thoracic Society criteria (13)(14) {Formatting Citation} (Spirometer CPX, Cardinal Health, Hoechberg, Germany). Then, they performed a resting electrocardiogram (QRS Universal ECG, QRS, Plymouth, MN, USA). P_{lmax} was measured during a maximal, static inspiratory effort measured at the mouth (Micro RPM, Micro Medical Ltd., Chatham, Kent, UK). P_{lmax} was recorded as the highest value averaged over 1s from three maneuvers that varied by less than 10% and was measured based on three maximal reproducible respiratory efforts. Then, an incremental test on treadmill (Technogym Run Race 1400HC, Gambettola, Italy) was performed to determine the VO_2 peak (Circuit Spirometry Vmax 29C, Sensormedics, USA). While performing the tests, the cardiac response was measured every 10s (JECG 12 Canal, Friedberg, Alemania). Blood oxygen saturation percentage (Ear oximeter, Hewlett-Packard 47201A, Corvallis, EEUU) and respiratory gas exchange were measured every 5 sand breath by breath respectively, throughout the test. Finally, one week apart, the patients performed the 6MWT according to the ATS guideline (15).

All tests were performed according to a standardized protocol before starting the training and 2 days after its completion.

Training program

Participants carried out a supervised RP for 8 weeks, 3 days per week. The training sessions lasted 60 minutes and included a warming up phase, a main phase and a recovery phase. After each session, Borg's perceived exertion was measured. The RP included aerobic exercise on cycle ergometer and on treadmill (progressing since 10' to 30' and since 40 to 75% of the reserve heart rate (RHR) or 6-7 score based on Borg's perceived exertion), strengthening of lower and upper limb muscles groups, breathing exercises (pursed lip breathing, diaphragmatic and abdominal breathing and diaphragmatic mobility) and finally stretching exercises.

In the FB group, for restricted nasal breathing, at the beginning of the training program, the small size device was used (4 mm). The size of the device was progressively increasing according to the patient adaptation to the 5 or 6 mm device,

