depending on the score on Borg's perceived exertion scale. If the patient has a score under 4 after the RP sessions the size of the FB device was increased.

FB was placed under the nostrils, using sterile gloves and assessing the patient did not have mucus or injuries. The device was used during the RP and patients were invited to have a physiological breathing by nasal inspirations and mouth expirations.

Statistical Analysis

Descriptive data of the participants are expressed as mean \pm standard deviation or number and percentage for continuous and categorical variables respectively. Percentage of change (%_{Change}) for each variable was calculated as:

$$\%_{\text{Change}} = (\text{mean(Post-test value)} - \text{mean(Pre-test value)}) / \text{mean(Pre-test value)} * 100$$

Differences among RP (between differences) and between pre- and post RP tests within each breathing condition (within differences) were analysed using a Bayesian hierarchical model. 6MWT distance, P_{lmax} and CAT were considered as continuous variables while mMRC dyspnea was treated as an ordinal variable. To analyse differences at baseline only a categorical variable indicating the RP (GC, ONB or FB) was introduced in the model as predictor. However, to analyse both between and within differences RP, time (pre- or post-PR) and their interaction were introduced as predictor variables. Due to the sample size in our study we choose to analyse our data using Bayesian inference since it has proven to be a proper method of statistical inference for small sample size (16)(17). Inference was performed based on the 95% credible interval (95% CrI) which contains a range of values where we can be 95% certain that the true value lie given the data at hand and the model fitted. The Bayesian hierarchical model was fitted using the package *brms* for the R programming language for statistical computing and graphics (18). All parameters estimated showed a good convergence with values of $\hat{R} = 1$ and number of effective sample size > 1000 . Further analysis can be found in the supplemental file while the code and the dataset to replicate it are stored in https://github.com/[name]/COPD_2_1.

References

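### Between-arm effects come from an RP × time model without baseline adjustment and with the contrast unnamed; adjusting for the pre-test value would usually be more precise

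*Combined protocol and SAP*

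**What the plan says.** The Statistical Analysis section uses one Bayesian hierarchical model for both arm comparisons and pre-post comparisons: "to analyse both between and within differences RP, time (pre- or post-PR) and their interaction were introduced as predictor variables". Time has a pre level, so the pre-test value enters as an outcome row. The arm comparison is introduced only by the phrase "Differences among RP (between differences", and no contrast is defined. Baseline is otherwise used only in a separate comparison of the arms: "To analyse differences at baseline only a categorical variable indicating the RP (GC, ONB or FB) was introduced in the model as predictor". No baseline covariate and no common baseline mean is mentioned.

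6MWT distance, PImax and CAT are modelled as continuous, while "mMRC dyspnea was treated as an ordinal variable". The choice of method is tied to trial size ("Due to the sample size in our study we choose to analyse our data using Bayesian inference"), and inference rests on 95% credible intervals. For more detail the reader is sent elsewhere: "Further analysis can be found in the supplemental file while the code and the dataset to replicate it are stored in" an online repository. Neither the supplement nor the code was available for this review.

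Under Design, patients are randomised to FB, ONB or CG, and "All tests were performed according to a standardized protocol before starting the training and 2 days after its completion". Under Participants, 36 patients are included. The document gives no arm sizes, SDs, pre-post correlation, power or precision figure.

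**The concern.** With a separate baseline mean for each arm, the model can yield two between-arm effects: the RP × time interaction (difference in change) or the difference at post-test. The interaction makes the first the likelier reading, but the text does not say so. On the same complete data, the two answers differ by exactly the chance baseline gap between the arms, so a reader cannot tell which FB-ONB result is reported.

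Neither contrast makes the best use of the pre-test value. The post-test difference ignores it. The change score in effect fixes its slope at 1. Estimating the slope usually gives a more precise contrast. A plan that cites its small sample as the reason for its method, and draws conclusions from interval width, has good reason to use this information, which it already collects.

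**Working it through.** There is no precision figure in the document to reproduce, so the check compares the variances of the candidate contrasts.

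**From the document:** 36 patients, three randomised arms, one pre-test and one post-test.

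**Assumed:** n = 12 per arm, complete data, weak priors, a patient-level term in the hierarchical model, pre-test SD = 1, post/pre SD ratio k, correlation ρ, and the same slope in every arm unless stated.

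**Variance of a difference between two arms**
- Post-test: 2k²/n
- Change: 2(1 + k² − 2ρk)/n
- Adjusted for pre-test: [2k²(1 − ρ²)/n] × 32/31. The factor is 1 + 1/(33 − 2), the price of estimating one slope with 36 − 3 = 33 within-arm degrees of freedom.

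Example with k = 1 and ρ = 0.7: post-test 2/12 = 0.167; change 2(0.6)/12 = 0.100; adjusted 2(0.51)/12 × 32/31 = 0.0877. The ratios are 0.0877/0.100 = 0.88 and 0.0877/0.167 = 0.53.

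| Adjusted variance relative to | ρ = 0.5 | ρ = 0.7 | ρ = 0.9 |
|---|---|---|---|
| change, k = 1 | 0.77 | 0.88 | 0.98 |
| change, k = 0.8 | 0.59 | 0.65 | 0.63 |
| change, k = 1.25 | 0.92 | 1.01 | 0.98 |
| post-test, any k | 0.77 | 0.53 | 0.20 |

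Simulation (120,000 trials per setting) agreed within about 0.01. For k = 1, mean interval-width ratios against the change score were 0.88, 0.94 and 0.99, and were unchanged to two decimals with arms of 14, 12 and 10. These used t intervals as a stand-in for credible intervals under weak priors.

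**Limit of the loss with a common slope.** The change variance minus the adjusted variance before the 32/31 factor is 2(1 − ρk)²/n, which is never negative. Adjustment can therefore cost at most 1/31, about 3%. That is reached when ρk = 1, for example k = 1.25 and ρ = 0.8, where the ratio is 1.03. With k = 1, adjustment beats both unadjusted contrasts for ρ from about 0.18 to 0.94.

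**Unequal slopes.** CG receives no training, so its slope may differ.
- Case A: k = 1, ρ = 0.9 in FB and ONB, 0.6 in CG. The pooled slope is (0.9 + 0.9 + 0.6)/3 = 0.8. The adjusted FB-ONB estimate then shifts by (0.9 − 0.8) = +0.10 per unit of baseline gap. Adjusted/change variance is 1.06 for FB-ONB and 0.90-0.91 for the two contrasts with CG.
- Case B: ρ = 0.9 and k = 1.11 in FB and ONB; ρ = 0.7 and k = 1 in CG. The ratios are 1.09 for FB-ONB and 0.98 for the others, with the same shift of about +0.10.
- Arm-specific slopes read at the overall baseline mean remove the shift and give FB-ONB ratios of 1.02 (A) and 1.07 (B). If slopes are in fact common and k = 1, this version gives 0.80, 0.91 and 1.02 at ρ = 0.5, 0.7 and 0.9.

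**Size of the ambiguity.** The post-test answer minus the change answer equals the baseline gap. Its SD is √(2/12) = 0.41 patient SDs. In 150 frequentist random-intercept RP × time fits, the RP coefficient with pre as reference equalled the raw baseline difference, and RP plus interaction equalled the raw post-test difference, to rounding error.

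**The case against.** RP, time and their interaction form a standard, valid analysis of a randomised pre-post design, and adjustment is an efficiency preference. The difference in change is the likelier reading, and the section's percentage-change formula supports it. Against that contrast the gain is modest, and the large ratios (0.53, 0.20) concern the less likely reading. The supplement or code may name the contrast. The comparison that isolates the device is FB-ONB, which is where a pooled slope did slightly worse in cases A and B. Interval width may not show that loss: with pooled-variance t intervals the FB-ONB width ratio was 0.965 in A and 1.00 in B. Finally, "All parameters estimated showed a good convergence" shows that models have already been fitted, so new contrasts are post hoc.

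Most of this stands as a limit on weight. The documents cannot place the trial within the assumed range. The FB-ONB loss is real in those two cases, and it is why the arm-specific-slope check is needed. The width result in A does not mean the adjusted interval is too narrow. The pooled change variance per patient is (0.2 + 0.2 + 0.8)/3 = 0.40 against 0.20 for FB and ONB, so both pooled intervals are wide for that pair.

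None of this removes the two facts at issue: the text names no contrast, and the listed predictors include no baseline adjustment. The RP main effect is a third possible reading, but with pre as the reference level it is only the baseline difference.

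**Conclusion.** The concern holds, as a recommended improvement and not as an error. Both unadjusted contrasts are unbiased under randomisation.

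Against the difference in change, adjustment narrows intervals by about 12%, 6% and 1% at ρ = 0.5, 0.7 and 0.9 when SDs are equal. It gains more if the SD falls after training and little or nothing if it rises. Against the post-test difference the gain is clear from ρ = 0.5 upwards. The cost is at most about 3% in variance with a common slope, and was 6% to 9% for FB-ONB with a pooled slope in the two unequal-slope cases. No general bound is claimed when slopes differ.

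Arm sizes, ρ, SD ratio, complete data, weak priors and a patient-level term are all assumptions, so confidence is medium. The figures apply to 6MWT distance, PImax and CAT. They do not carry over to ordinal mMRC, where adjustment also changes the effect to a conditional one. The common-baseline longitudinal model recommended below as an alternative was not simulated.

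**What to change.** 1. State in Statistical Analysis which between-arm contrast is reported.
2. For 6MWT distance, PImax and CAT, estimate FB-ONB, FB-CG and ONB-CG from a model of the post-test value on arm and the patient's own pre-test value. A longitudinal model with one common baseline mean and separate pre and post variances is an alternative.
3. As a check, show the version with arm-specific slopes read at the overall baseline mean.
4. Keep the RP × time model for within-arm changes. Adjusting mMRC for its baseline in an ordinal model is optional.
5. Label the adjusted analysis as revised and show it beside the RP × time results already obtained.

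The cost is one sentence, plus one model formula and one slope for each of three outcomes; the arm-specific check needs a further fit. No new data are required. The report gains 3 × 3 = 9 further contrasts chosen after models were fitted, which is why the labelling matters.
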